14.4 Missing, Unused & Spurious Data

Details will be provided in the Statistical Analysis Plan (SAP).

14.5 Procedures for Reporting Deviation(s) from the Original SAP

These will be submitted as substantial amendments where applicable and recorded in subsequent versions of the protocol and SAP.

14.6 Termination of the Trial

This is a low risk feasibility study thus no early stopping rules will be specified.

14.7 Inclusion in Analysis

All eligible participants will be included in the assessment of feasibility. All participants providing secondary outcome data will be included in those analyses.

15 Analysis

15.1 Main Analysis

Key demographic data will be summarised using descriptive statistics. For feasibility outcomes, recruitment will be assessed as the percentage of eligible people who provide consent to participate in the trial; retention as the percentage of participants recruited who complete the 12-week follow-up assessment; adherence as the percentage of recommended intervention or social control sessions completed. Feasibility criteria will be assessed according to a traffic light system with green (proceed to full effectiveness RCT) if all criteria listed in section 5.3 are in the green zone; amber (requiring adjustment before proceeding to full RCT) if all criteria are either in the amber or green zone; and red (do not progress to full RCT unless major changes are implemented) if at least one criterion is in the red zone. For secondary outcome measures we will calculate descriptive summaries such as mean and standard deviation, and 95% confidence intervals of participants' percentage changes from baseline to 12-week follow-up. This will provide estimates of effect size and variability of drumming-induced changes for use in power calculations for a future RCT.

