5.3 Primary Outcome Measure

Feasibility of participant recruitment and retention and intervention adherence according to prespecified criteria

	Progression Criteria				
		Red	Amber	Green	
Recruitment	No. approached willing to participate				
	(number consented/ number				
	approached)	<5%	5-19%	≥20%	
		< 24 in			
	No. recruited	total	25-44	45-60	
Retention	No of participants completing primary				
	end point	<50%	51-89%	≥90%	
	% Participants adherent to the				
Adherence	intervention (as defined in section 11.1)	<50%	51-79%	≥80%	
	% Participants completing at least 90%				
	of available baseline measures	<70%	71-94%	≥95%	
Data	% Participants completing at least 90%				
Completeness	of follow up measures	<50%	51-74%	≥75%	

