9.1 Participant Identification

Participants will be identified in a range of secondary care provisions and movement clinics that cater for people diagnosed with PD, which include neurology and care of the elderly. Clinical staff (consultants, nurses and PD specialist nurses) will identify potential participants for recruitment alongside social media and advertising through local PD focussed organisations such as Parkinson's UK Cymru. Participants may also self-refer by contacting the trial team on the advertised e-mail address.

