9.2 Screening Logs

A screening log of all ineligible and eligible but not consented and/or not approached individuals will be kept at each site so that any biases from differential recruitment can be detected. When at site, logs may contain identifiable information but this **must** be redacted prior to being sent to the CTR. The screening log should be sent to the SParky Samba Trial email every month (see section 16 for further detail on data monitoring/quality assurance).

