11.3 Adherence

Participants will be emailed a link to the REDCap database each week following the session to complete a self-report attendance checklist.

Group facilitators will also be asked to complete a checklist following each session during the recruitment and intervention delivery period.

12 Trial Procedures

Recruitment and follow-up:

Participants will be identified at clinical sites or via social networks/ word of mouth and eligible participants will be approached and provided with trial information prior to giving informed consent. Participants will be assessed at baseline and at 12 weeks post randomisation following intervention delivery. The intervention delivery period will commence at randomisation (to occur within 2 weeks of baseline assessment) and will last for a period of 12 weeks. With the addition of the process evaluation (see below), participants are expected to be in the trial for no longer than 16 weeks.

Data collection/assessments and blinding

Outcome data will be collected through a combination of patient reported measures completed directly within the database and in person assessments conducted by research staff at site. If a participant choses, they will be able to complete the patient reported outcomes on paper copies if they prefer (see data management section 16.2). participants may be supported with on-line or paper completion at the hospital research visit by the trial research staff, or at home by one of the core trial team members via telephone. Due to the nature of the intervention and the pragmatic design of the trial, researchers collecting assessment data will not be blind to the allocation of participants. In an effort to reduce bias of rating the UPDRS, this assessment will be videoed by the assessor at site and rated independently by an expert blinded to allocation. The measures included in SParky Samba do not form part of routine care, although PD specific measures such as UPDRS and Hoen and Yahr may be used by clinicians ad-hoc as part of their routine assessment of participants at clinic appointments.

Intervention (and intervention comparator) adherence data will be provided through participant self-report and self-report from SParky Samba group facilitators.

Process Evaluation:

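### The recruitment-rate progression criterion has two denominators, people approached (Section 5.3) and eligible people (Section 15.1), and the choice can change its colour

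*Protocol*

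**What the plan says.** Protocol Section 5.3 makes recruitment, retention and adherence the primary outcome, judged against prespecified criteria. The first recruitment row of its table is "No. approached willing to participate". The formula beside it is consents divided by people approached, with red below 5%, amber 5-19% and green from 20%.

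Section 15.1 describes the same outcome differently: "recruitment will be assessed as the percentage of eligible people who provide consent to participate in the trial". The same paragraph then sets the overall result as "green (proceed to full effectiveness RCT) if all criteria listed in section 5.3 are in the green zone", and as "red (do not progress to full RCT unless major changes are implemented) if at least one criterion is in the red zone".

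Three other places bear on who is counted:

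- Section 9.2: "A screening log of all ineligible and eligible but not consented and/or not approached individuals will be kept at each site".
- Section 9.1: "Participants may also self-refer by contacting the trial team on the advertised e-mail address". This is in addition to clinic staff, social media and charity advertising.
- Section 12, on recruitment and follow-up, says of people identified at clinical sites or through social networks and word of mouth that "eligible participants will be approached and provided with trial information prior to giving informed consent".

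**The concern.** One primary criterion carries two formulas. The log in Section 9.2 covers people who are ineligible and people who were not approached, so the protocol itself expects the approached and the eligible to be different groups. The eligible-based rate is the lower of the two if some eligible people are never approached. It is the higher if some approached people turn out to be ineligible.

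The overall rule gives this row full weight: it can block a green result alone, and a red here makes the whole trial red. If both formulas stand, the colour could be settled after the counts are known, which is what prespecified criteria are meant to prevent.

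Neither formula says how self-referrers are counted. If they enter only the numerator, the rate is inflated. If they enter both, people who came forward themselves are pooled with people invited in clinic, and the pooled rate may hide a lower uptake in clinic.

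**Working it through.** **The plan's own figure.** Section 14.3 gives a 95% interval of at most ±13 percentage points for the feasibility rates. With n = 60 and p = 0.5, 1.96 × √(0.25/60) = 0.1265, or 12.65 points, so the figure reproduces. It is based on the 60 recruited and does not show which denominator the recruitment rate should use.

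**Inputs.** Consents: 60, the recruitment target (Sections 6 and 9.3). Cut-offs: 5% and 20% (Section 5.3). The protocol gives no expected numbers approached, eligible or self-referred, so every such count below is an assumption.

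**When the colour changes.** For a denominator D the rate is 60/D. It is green when D ≤ 60/0.20 = 300 and red when D > 60/0.05 = 1200. The two definitions give different colours when 300 or 1200 lies between the number approached and the number eligible.

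| Assumed situation | Consented / approached (5.3) | Consented / eligible (15.1) |
|---|---|---|
| 400 eligible, 240 approached | 60/240 = 25.0%, green | 60/400 = 15.0%, amber |
| 1300 eligible, 1040 approached | 60/1040 = 5.8%, amber | 60/1300 = 4.6%, red |
| 350 approached, 280 of them eligible | 60/350 = 17.1%, amber | 60/280 = 21.4%, green |
| 1250 approached, 1000 of them eligible | 60/1250 = 4.8%, red | 60/1000 = 6.0%, amber |
| 250 eligible, 200 approached | 60/200 = 30.0%, green | 60/250 = 24.0%, green |

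Rows 1 and 2 have eligible people who were not approached. Rows 3 and 4 have approached people who proved ineligible. Row 5 shows no change of colour.

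**Self-referrers.** Suppose 250 people are approached in clinic and 40 consent, and 20 more consents come from self-referral.

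- Clinic only: 40/250 = 16.0%, amber.
- Self-referrers in the numerator only: 60/250 = 24.0%, green.
- Self-referrers in both, all 20 consenting: 60/270 = 22.2%, green.
- Self-referrers in both, N given information and 20 consenting: 60/(250 + N) stays at or above 20% while N ≤ 50. The pooled rate is therefore green as long as at least 20/50 = 40% of them consent.

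Pooling does not always change the colour. With 200 approached in clinic, 40/200 = 20.0% and 60/220 = 27.3% are both green. With 400 approached, 40/400 = 10.0% and 60/420 = 14.3% are both amber.

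**The case against.** The best defence is that Section 15.1 ties the colours to the criteria listed in Section 5.3, where the bands stand next to an explicit formula. On that reading the approached denominator decides the colour and Section 15.1 only describes the measure loosely. This is a good reason to keep the Section 5.3 formula. It does not remove the conflict, because Section 15.1 states how recruitment will be assessed and neither section is given precedence. Nor can it simply be left to the SAP: with two definitions in the protocol, a SAP would have to contradict one of them.

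Section 12 says that eligible people will be approached, including those found outside clinic. That narrows the gap between the denominators. It does not close it, since Section 9.2 provides for people not approached and Section 12 does not define the count.

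A reader might also infer more than the text supports:

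- *That self-referrers are never approached and so have no denominator.* Section 12 allows them to be counted as approached once they receive trial information. Section 16 also lists electronic sources besides the screening log for the feasibility outcomes, so the protocol does not show that self-referrers go uncounted.
- *That self-referrers have already decided and nearly all consent.* The protocol does not say so. They may enquire and then decline.
- *That the bands should apply to clinic patients only.* The protocol recruits by mixed routes on purpose and sets one band for them. It does not say that a full trial would drop advertising or that this rate is meant to plan clinic screening. A clinic-only rule would be a third definition and is a design preference.

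It is also fair to say that the number recruited has its own criterion, that amber means adjustment and not stopping, and that no interim analysis or stopping rule uses this rate. These limit the harm. They do not settle which rate is compared with the bands.

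**Conclusion.** The conflict between Sections 5.3 and 15.1 is real and should be resolved before the rate is calculated, because it affects the definition of a primary progression criterion. The two definitions can give different colours at either cut-off and in either direction: 25% against 15% at the upper one, and 5.8% against 4.6% at the lower one, on assumed counts with 60 consents. A change of colour is possible, not certain. It needs 300 or 1200 to fall between the numbers approached and eligible, and the protocol gives no expected values from which to judge how likely that is.

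The self-referral point is secondary. The protocol leaves open how these people are counted, and pooling them can raise the overall rate. How far depends on their number and their consent rate, which are unknown.

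**What to change.** 1. Use one definition in both sections. The simplest change is to amend Section 15.1 to the Section 5.3 formula, consents divided by people approached, because the bands are attached to it. State that numerator and denominator cover the same people.
2. State that a self-referrer counts as approached once given the trial information.
3. Record the source of referral for everyone approached, and keep a simple log of enquiries to the trial e-mail address.
4. Report uptake overall against the bands, and separately for clinic-approached and self-referred people. Both routes continue to count towards the number recruited.

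Restricting the bands to clinic patients is optional and not needed to resolve the conflict.

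The cost is a wording change in the protocol, one data field and an enquiry log. No visit, assessment or sample size changes.

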5.2 Secondary Objectives

 Explore the effect of the SParky Samba intervention as compared to an active social control across function and wellbeing of people with PD.

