11.1 SParky Samba Intervention

SParky Samba is a samba-based rhythm/ drumming intervention delivered within the community for people with PD. The setting is determined by local availability of facilities, which are chosen by SParky Samba leaders based on their geographic location and accessibility for group members.

The group is facilitated by either a local Samba musician, or a regular member of the group who has been trained by the musician to deliver SParky Samba sessions. The group size is usually around 8-15 participants but there is no minimum or maximum number of participants required for any given session.

In their first session participants will be offered a choice of instrument that is suitable for their range of motion. This could range across tamborims, Snare drums (Caixa), Agogo bells, Surdos, Ganzás / Chocalho (shakers), Cuíca, Timbal, Pandeiro, and the Repinique.

During each session, participants will be instructed to follow a sequence of rhythms, as guided by the facilitator. Each rhythm is broken down into smaller sections with sub-groups (grouped by instrument) concentrating on their own section before coming together. The band leader often carries a Repinique, as well as using Apitos (whistle) to signal breaks to participants.

Each session will last approximately 60 minutes with time either side for the set-up and break down of instruments and seating.

Participants will be asked to attend as many sessions as possible, ideally weekly over a period of 12 weeks following randomisation. Participants will be encouraged to attend at least 6 consecutive sessions and a minimum of 8 in total (completion of 8 sessions in total will be regarded as adherent to the intervention). The costs of participant travel to attend Sparky Samba sessions will be reimbursed. Alternatively, travel arrangements will be made upfront on behalf of the participant if they prefer.

The PPI Group have been involved in the co-production of patient facing materials and the intervention definition through a series of stakeholder workshops that have informed phase 2 of the trial. The trial team will continue to work with the PPI Group throughout the trial in co-production of documents for publication and an Intervention Manual.

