11.2 Intervention Comparator

Participants randomised to the activity as usual control group will be asked to continue with their normal activities and attend any social or support groups they would normally attend over the 12 weeks. Following completion of the 12-week follow-up assessment they will be offered the opportunity to join their local SParky Samba group.

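### Adherence, a primary progression criterion, counts participants in sections 5.3 and 11.1 but sessions in section 15.1, where the control part has no denominator

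*Protocol*

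**What the plan says.** - **Protocol 5.3** makes adherence a progression criterion within the primary outcome. The row counts participants who are adherent to the "intervention (as defined in section 11.1"). Red is below 50%, amber 51 to 79%, green 80% or more.
- **Protocol 11.1** makes this a yes/no status: "completion of 8 sessions in total will be regarded as adherent to the intervention". On the number of sessions it says "Participants will be asked to attend as many sessions as possible, ideally weekly over a period of 12 weeks following randomisation", and also "Participants will be encouraged to attend at least 6 consecutive sessions and a minimum of 8 in total".
- **Protocol 15.1** states how the feasibility outcomes will be assessed and gives "adherence as the percentage of recommended intervention or social control sessions completed". Its next sentence applies the traffic light to the criteria of section 5.3. One red criterion makes the overall result red, meaning no full trial without major changes. Overall green needs every criterion green.
- **Protocol 11.2** says that controls "will be asked to continue with their normal activities and attend any social or support groups they would normally attend over the 12 weeks". The synopsis and sections 6 and 9.5.2 also describe activity as usual. Section 5.2, however, speaks of the intervention "as compared to an active social control across function and wellbeing of people with PD", and section 12 expects adherence data for the comparator.
- **Protocol 14.3** promises a 95% interval within ±13 percentage points for recruitment, retention and adherence.

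**The concern.** The two definitions differ in three respects: the unit (participants or sessions), the 8-session threshold (present or absent) and the population (intervention arm or both arms). The colour bands stand on the participant row of 5.3. Section 15.1 gives a session percentage and then applies those bands without saying how the two relate.

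The control half of the 15.1 definition cannot be calculated, because the protocol neither delivers nor recommends sessions to controls.

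At stake is the colour of one primary criterion and, through the any-red and all-green rules, possibly the overall recommendation. A SAP that follows either definition would contradict the other section, so this is not detail that the protocol has merely deferred.

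**Working it through.** **The plan's own figure.** The ±13 points of section 14.3 follow from the normal-approximation half-width at its maximum, p = 0.5:

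1.96 × √(0.25/60) = 12.65 points.

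The figure therefore reproduces with all 60 participants as denominator. Adherence to SParky Samba concerns the 30 allocated to it (synopsis):

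1.96 × √(0.25/30) = 17.89 points, about ±18.

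**Inputs for the colours.** There are 30 intervention participants (synopsis), a threshold of 8 (11.1) and the bands of 5.3. The number of recommended sessions is not fixed. It can be read as 12 (weekly for 12 weeks) or as 8 (the minimum), so both are shown. The attendance patterns are assumptions, not trial data.

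**Formulas.** Let s be the sessions attended by one participant.

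- 5.3 with 11.1: number with s ≥ 8, divided by 30.
- 15.1, 12 recommended: sum of s, divided by 12 × 30 = 360.
- 15.1, 8 recommended: sum of the smaller of s and 8, divided by 8 × 30 = 240.

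**Results.**

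| Assumed attendance | 5.3 with 11.1 | 15.1, of 12 | 15.1, of 8 |
|---|---|---|---|
| All 30 attend 8 | 30/30 = 100%, green | 240/360 = 66.7%, amber | 240/240 = 100%, green |
| All 30 attend 7 | 0/30 = 0%, red | 210/360 = 58.3%, amber | 210/240 = 87.5%, green |
| 12 attend 12, 18 attend 7 (40%, 60%) | 12/30 = 40%, red | 270/360 = 75.0%, amber | 222/240 = 92.5%, green |
| 24 attend 8, 6 attend none | 24/30 = 80%, green | 192/360 = 53.3%, amber | 192/240 = 80%, green |
| 23 attend 12, 7 attend 7 | 23/30 = 76.7%, amber | 325/360 = 90.3%, green | 233/240 = 97.1%, green |
| 20 attend 12, 10 attend none | 20/30 = 66.7%, amber | 240/360 = 66.7%, amber | 160/240 = 66.7%, amber |

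The last row shows that the definitions can agree. The others show that they can differ, and in either direction.

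**Why they differ.** Green under 5.3 with 11.1 needs 24 of 30 participants to reach 8 sessions. Green under 15.1 needs mean attendance of 0.8 × 12 = 9.6 sessions, or mean capped attendance of 0.8 × 8 = 6.4. These are different requirements under one label. A group in which everyone completes exactly 8 sessions is fully adherent by 11.1, yet cannot be green under 15.1 if 12 is the denominator.

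**Control arm.** The numerator would be the usual groups attended. The denominator would be the sessions recommended, and section 11.2 gives no such number. The ratio is undefined.

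**The case against.** The strongest reply is that the text already leads to one definition. The traffic-light sentence in 15.1 refers to the criteria of 5.3, the 5.3 row names participants and cites 11.1, and 11.1 sets 8 sessions. No band is labelled for a session percentage, and the row concerns adherence to the intervention, so the control wording never enters it. This is the more natural reading and it lowers the risk. It does not remove the conflict: 15.1 presents the session percentage as the way adherence will be assessed, does not call it descriptive, and grades in the next sentence.

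The two-arm wording is also not isolated. Section 12 plans comparator adherence data, and the precision in 14.3 fits adherence only if all 60 participants count.

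Three stronger readings may tempt a reader, and the document does not support them:

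- That one red criterion ends progression. Red is conditional: a full trial may still follow if major changes are made.
- That controls attend no social sessions at all. They may attend their usual groups. The point is only that none are delivered or recommended, so nothing can serve as denominator.
- That the definition would be picked once attendance is known. The SAP is not at hand and may settle the definition beforehand. The protocol shows a contradiction, not a selective choice.

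It is also fair to say that uniform attendance is artificial. The mixed patterns in the table do not depend on it.

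**Conclusion.** The contradiction is real and concerns a primary feasibility criterion. Read literally, 15.1 pairs the 5.3 bands with a measure for which they were not written and includes a control component that cannot be computed. Under the assumed patterns the colour moves by one step if 12 sessions are recommended (for example red to amber, or green to amber), and by up to two steps, red to green, if 8 are. The size depends on the actual spread of attendance, and some patterns give no difference. The cross-reference from 5.3 to 11.1 makes the 8-session definition the likely intention, but the protocol should state it.

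Once adherence is confined to the intervention arm, the ±13 points of 14.3 no longer hold for it: the maximum half-width is about ±18 points. Whether 8 sessions is the right threshold is a separate matter and is not judged here.

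**What to change.** 1. In 15.1, state adherence as the percentage of participants randomised to SParky Samba who are adherent as defined in section 11.1, which is the definition that 5.3 already cites. Delete the reference to control sessions.
2. Report the number of sessions attended, and usual activity in the control arm, as descriptive items with no traffic light.
3. Reconcile the description of the control in 5.2, and the comparator adherence data in section 12, with the activity-as-usual control of section 11.2.
4. In 14.3, confine ±13 points to rates with all 60 participants as denominator, and give about ±18 points for adherence (n = 30).

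The cost is a few sentences in the protocol, carried into the SAP. No new data are needed, because the weekly attendance checklist in 11.3 already supplies the counts. The one downside is that the stated precision for adherence becomes less favourable.

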8.1 Inclusion Criteria

- People diagnosed with PD.
- Age 18 or older
- Able to provide consent to take part

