12.1 Assessments

Table 2. SParky Samba Outcome Assessments

Construct	Measure	Time to complete	Time points
Motor	UPDRS III: We will use section III of the Unified Parkinsons Disease Rating Scale to assess global motor function in participants	15 min	Baseline and 12 weeks
	Freezing of Gait questionnaire (FOG) : this is a patient self report measure designed to assess the severity of gait freeing in people with PD.	5 min	Baseline and 12 weeks
	Dresden Falls Questionnaire — this is a patient report questionnaire designed to assess the risk and severity of falls, a common symptom in people with PD.	5 min	Baseline and 12 weeks
	MiniBEST Test in this assessment participants are assessed across dynamic balance, functional ability and gait.	15 minutes	Baseline and 12 weeks
	Physical Activity in the Elderly (PASE) questionnaire this questionnaire is designed to capture the level of physical activity across a range of usual activities over the past 7 days.	5 min	Baseline and 12 weeks
Cognitive	Montreal Cognitive Assessment (MoCA) – we will use the truncated on- line version of the MoCA, known as Expresso, to assess cognitive function in participants. This is well validated for assessing cognitive function in pe	6 minutes	Baseline and 12 weeks
Quality of Life	Parkinson's Disease Quality of Life Questionnaire [8 items] – PDQ-8; This is a self-completion participant reported outcome designed to address aspects of functioning and well-being for those affected by Parkinson's disease. The PDQ-8 asks one question from each of the domains of the longer PDQ-39; activities of daily living, attention and working memory, communication, depression, quality of life and social relationships.	5 minutes	Baseline and 12 weeks
Self Efficacy	Oxford Participant and Activities Questionnaire (OxPaq)— this is a validated self-report questionnaire designed to assess the degree of activity and participation of those with chronic conditions taking part in community based interventions	5 minutes	Baseline and 12 weeks
	The Lorig Self Efficacy (scale will be utilised to measure self-efficacy related to exercise (exercise sub-scale only)	5 minutes	Baseline and 12 weeks

Figure 3. Schedule of enrolment, interventions and assessments

Procedures	Visits (insert visit numbers as appropriate)

	Baseline V	isit (week 0)	Intervention	Follow Up Visit (week 12 ± 5 days)			
	At home (Day -3;	At hospital (Day 0)	Delivery (Day 0 – Day 84)	At home (Day 85	At hospital Day 88 ±2		

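### The only planned confidence intervals for the secondary outcomes are on percentage change from baseline, which is undefined at a zero baseline and averages above zero when nothing has changed

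*Protocol*

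**What the plan says.** Protocol section 15.1 plans descriptive summaries such as the mean and SD for the secondary outcomes, together with 95% confidence intervals for the "percentage changes from baseline to 12-week follow-up" of the participants. It then states the purpose: "This will provide estimates of effect size and variability of drumming-induced changes for use in power calculations for a future RCT". It names no absolute change, no baseline-adjusted 12-week score and no between-arm difference.

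The nine secondary outcomes (section 5.4) include a freezing of gait questionnaire, described in section 12.1 as "this is a patient self report measure designed to assess the severity of gait freeing in people with PD", and a falls questionnaire, described there as "this is a patient report questionnaire designed to assess the risk and severity of falls, a common symptom in people with PD". The clinical entry condition in section 8.1 is "People diagnosed with PD"; the other criteria are adult age and capacity to consent. No minimum stage, freezing or history of falls is required.

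On the analysis set, section 14.7 says: "All participants providing secondary outcome data will be included in those analyses". Section 14.4 leaves missing, unused and spurious data to the SAP, and section 15.1.1 leaves sub-groups to it. The choice of percentage change is not deferred; the protocol makes it.

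**The concern.** Percentage change divides each participant's change by that participant's own baseline. Two problems follow.

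First, a baseline of zero gives no value, and a baseline near zero gives an extreme one. People without freezing or falls are eligible and would be expected to score at or near the bottom of those two scales. The inclusion rule in section 14.7 cannot then be met for them on the planned measure.

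Second, the measure treats rises and falls unequally. A score going from 4 to 2 counts as -50%, and one going from 2 to 4 counts as +100%. The mean of the two is +25% although the group mean has not moved.

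At stake are the numbers that the study is meant to hand to the next trial. A power calculation for a trial analysed in scale units needs a difference and an SD in those units, and preferably the baseline to follow-up correlation. None of these can be recovered from a mean and SD of percentage changes.

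**Working it through.** **The plan's own figures.** The protocol gives no SD, correlation or score range for any secondary outcome, so there is no figure on this point to reproduce. Its only precision figure (section 14.3, at most 13 percentage points) concerns feasibility proportions. It reproduces as 1.96 × √(0.25/60) = 12.7 points and has no bearing here.

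**Inputs.** From the protocol: 60 participants, 30 per arm; green retention threshold 90% (section 5.3). Assumed: coefficient of variation (CV) 0.4 to 0.6, correlation ρ between visits 0.6 to 0.8, the share of zero baselines, and 27 followed up per arm (0.90 × 30).

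**Direction of the drift.** Let X and Y be positive scores at baseline and 12 weeks, exchangeable between visits (no change). Then E[Y/X] = E[(Y/X + X/Y)/2] ≥ 1, so the mean percentage change is at or above zero.

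**Size of the drift.** For lognormal scores with identical margins and raw-scale correlation ρ:

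mean percentage change = (1 + CV²)/(1 + ρ·CV²) − 1

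| CV | ρ | Calculation | Mean change |
|---|---|---|---|
| 0.4 | 0.7 | 1.16/1.112 − 1 | +4.3% |
| 0.5 | 0.7 | 1.25/1.175 − 1 | +6.4% |
| 0.6 | 0.7 | 1.36/1.252 − 1 | +8.6% |
| 0.4 | 0.8 | 1.16/1.128 − 1 | +2.8% (lowest) |
| 0.6 | 0.6 | 1.36/1.216 − 1 | +11.8% (highest) |

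**Other score shapes.** Simulated rounded normal scores (mean 30, CV 0.4) with no change gave a mean of +3.6% at correlation 0.9 and +13.3% at 0.6, with SDs of 39% and 94%. The median was 0, and the absolute change averaged between −0.01 and +0.01 points. On a simulated count scale with zero baselines dropped, the mean was +2.3% with 37% zeros and +12.3% with 20% zeros. Dropping zeros lets regression to the mean offset part of the drift.

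**Drift against sampling error.** Write R for 1 plus the mean change. In the lognormal model the SD of percentage change is √[(R² − 1)·R²]. At ρ = 0.7 this is about 31%, 39% and 46% for CV 0.4, 0.5 and 0.6. Dividing by √27 = 5.20 gives standard errors of about 6, 7 and 9 points, so the drift is about 0.7 to 1.0 standard errors.

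**Zero baselines.** If a share q scores zero, 60q participants have no value: 3, 6 or 12 of 60 for q = 5%, 10% or 20%. At q = 5% the chance of at least one is 1 − 0.95⁶⁰ = 95%. With 27 followed up per arm, shares of 20% and 50% leave 27 × 0.8 = 21.6 and 27 × 0.5 = 13.5 defined values.

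**The case against.** The strongest reply is that little depends on this. The secondary outcomes are exploratory, the study is not powered for them, and the traffic-light rule uses only recruitment, retention, adherence and data completeness. Raw scores are collected at both visits, so scale-unit summaries can be produced later from the same data. All of that stands, and it limits how serious the point is.

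Four stronger readings are tempting, and the protocol does not support them.

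- **That every planned summary is on the percentage scale.** The wording introduces the mean and SD as examples, and they may be meant as raw-score summaries. Only the confidence intervals, and what is drawn from them, are clearly percentage changes.
- **That participants with zero baselines will be excluded.** No exclusion is stated, and the SAP may deal with undefined values. What can be said is that the protocol has no rule.
- **That zero baselines affect all nine outcomes.** They are plausible for freezing and falls. For the PDQ-8, eight items across several domains, an exact zero is less evident. No score range is given for any scale.
- **That the drift would pass for a treatment effect between arms.** Randomised arms largely share it under no effect, so a contrast would mostly cancel it, and within an arm it lies inside the interval's half-width. Against this, section 15.1 specifies no contrast, although section 5.2 sets a comparison with control as the objective, and it describes the changes as caused by drumming.

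**Conclusion.** The point holds, confined to the confidence intervals and the planning values taken from them. The protocol itself fixes a measure that has no value at a zero baseline and whose mean sits about 3% to 12% above zero under no change. That range rests on lognormal scores, CV 0.4 to 0.6 and correlation 0.6 to 0.8. These inputs, the share of zero baselines, the score ranges and the 27 followed up per arm are all assumptions, because the protocol supplies none of them. The direction of the drift does not depend on the lognormal form, but it does need positive scores exchangeable between visits.

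This should be corrected before analysis because the intervals are meant to inform a later power calculation. It does not threaten the feasibility conclusions or the decision to progress.

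**What to change.** In section 15.1, and in the SAP to match, replace percentage change as the main summary of the secondary outcomes with:

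- mean and SD at baseline and at 12 weeks, by arm, in the scale's own units;
- absolute change with 95% CI, by arm;
- the between-arm difference at 12 weeks, adjusted for baseline, with 95% CI;
- the SD of the 12-week score and its correlation with baseline, as inputs to the future sample size.

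Percentage change may stay as a supplementary description, provided the text says how zero baselines are handled. The statement that the changes are due to drumming should then refer to the between-arm difference, read as exploratory.

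The cost is a short rewording. It needs no extra data, visits or participants.
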